Parkinson's disease (PD) is a common, debilitating neurologic disease. Over one million people suffer from PD in the United States alone. Deep brain stimulation (DBS) has been shown to be an effective treatment option. One of the most frequent targets for DBS in PD is the globus pallidus internus (GPi).

One limitation of surgical (e.g., DBS) treatment for PD is the inability to identify functional brain targets pre-operatively. Current methods rely on atlas-based approaches or coordinate-based stereotaxy where a specific coordinate, based on larger landmarks, is presumed to be the approximate location of the targeted functional region in all patients. These targeting methods rely on standardized coordinates that do not account for known inter-individual variations in functional anatomy. In fact, it has been previously reported that 46% of patients

with poor response to DBS therapy have malpositioned DBS leads.² There is also disagreement in the choice of ideal atlas-based coordinates. Perhaps most concerning regarding all methods of structural localization is the assumption that brain function is predictable by brain structure. The validity of such assumption is questionable as it has been shown that brain functional localization may vary significantly from predictions based solely on structure. It is now well-known that pathologic changes in the brain can result in variations in the relationship of structure and function due to neural plasticity.

The idea of brain connectomics is a rapidly developing field of neuroscience. The ability to examine *in vivo* human brain functional connectivity has revealed new insight into many neurologic and neuropsychological conditions. To date, the clinical impact of connectomics has been limited. The origin of the current proposal was the belief that this emerging technology could be applied to a very specific problem in clinical medicine not well-addressed by current techniques. As such, this project would ideally serve as a model and further proof that such science can be currently translated into clinical medicine.

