a. Study Design or Overview - Patients selected to undergo GPi DBS placement will be eligible for enrollment in the study. In addition to standard-of-care tests, subjects will undergo an MRI consisting of the proposed novel imaging protocol prior to placement of DBS. The patient will subsequently undergo standard-of-care therapy for DBS placement. Once the stimulator has been programmed post-operatively, the stimulation parameters and corresponding clinical changes will be collected and used to model the volume of activated tissue. The patient will additionally undergo a follow-up MRI used to localize the electrode within the brain to further localize the volume of activated tissue.

b. Study Subjects - Patients presenting to Mayo Clinic Neurosurgery identified to undergo deep brain stimulator placement in the GPi will be identified as potential subjects. Exclusion criteria for the proposed study would be any patient with contraindication to 3 Tesla MRI.

c. Sample Size - Due to the lack of any adequate preliminary studies, a sample size is estimated without statistical basis. A sample size of ten was chosen based on expected recruitment possibilities and sufficient size to prove feasibility and estimate power size for subsequent studies.

d. Data Collection -

Pre-Operative: Relevant clinical information will be collected including demographic data (age, gender), duration of Parkinson's disease, medication history, and a Unified Parkinson Disease Rating Scale (UPDRS) score. Pre-operative MRI will consist of a robust, multi-shell diffusion sequence at high resolution (1.5 x 1.5 x 1.5 mm voxel; b =1000, 2000; 64-directions, AP and PA phase encoding). Additional routine structural imaging consisting of T1-weighted MP-RAGE and FGATIR will also be obtained for purposes of identifying targets for segmentation.

Post-Operative: Clinical data will consist of post-treatment UPDRS score, complications related to DBS placement (e.g. infection, hemorrhage), and the stimulation parameters (voltage and contacts used) from the DBS programming to go with the tremor scoring. Stimulation parameters will also be recorded for any DBS programming that resulted in adverse effects, as well as the effect elicited. The patient will undergo an additional post-operative MRI using a T1 MP-RAGE sequence for purposes of localizing the final lead position.

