e. Data Handling - All data will be collected in an anonymized fashion with unique coded identifiers for each subject. The identifier linking to the patient will be stored in a separate password-protected spreadsheet for purposes of collecting data at each of the timepoints in the study.

Clinical data will be tabulated within an Excel spreadsheet that is also password protected and recorded by anonymized ID. The imaging data will be downloaded from the MRI scanner on an encrypted drive and transferred to a password-protected and encrypted Mayo Clinic computer only accessible to the PI. Imaging data will be collected and stored without patient identifiers, only by unique study ID. Processing of the imaging data will be performed and saved on the computer.

f. Data Analysis - MP-RAGE structural scans will be coregistered to the diffusion data and automatically segmented into regions of interest using FreeSurfer software. Regions of interest will consist of: (1) prefrontal cortex, (2) supplementary motor area, (3) premotor cortex, (4) primary motor cortex, (5) putamen, (6) caudate, (7) thalamus, (8) globus pallidus externus, (9) pedunculopontine nucleus, and (10) subthalamic nucleus.

The diffusion data will be used to determine voxel-wise diffusion parameters using a Markov Chain Monte Carlo sampling in the FMRIB Software Library (FSL) “bedpostx” function. A multi-fiber approach (2 fiber orientations) using a multi-shell model will be used. To perform GPi segmentation based on structural connectivity, we will utilize a probabilistic tractography method by way of FSL’s “probtrackx” to calculate probability of connection of each GPi voxel to the predefined volumes of interest (above). Each GPi voxel will then be assigned to the one target with the greatest number of propagated paths by using FSL’s “find_the_biggest” function.

Using the MP-RAGE and FGATIR MRI data, the target point for DBS placement will be determined using current standard of care. The amount of overlap between this target and each of the GPi functional segments will be calculated.

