The postoperative MRI scan will be coregistered to the pre-operative scans. The final location of the DBS lead will be calculated using LEAD-DBS software. Based on the stimulation parameters, the volume of activated tissue will be calculated with respect to lead localization. The amount of overlap between the volume of activated tissue (VAT) and each GPi segment will be calculated. Linear regression analysis will be performed to determine the degree of improvement in tremor score and degree of overlap between the VAT and each GPi segment. We hypothesize greater overlap between the VAT and GPi segment maximally connected to the primary motor cortex will result in a greater improvement in clinical improvement.

g. Feasibility and Time Frame – The expected timecourse for the study is one year. We would anticipate ~25 patients per year to be potential subjects based on historical figures of number of GPi DBS placements done at Mayo Clinic Florida. The timetable for each individual subject should be <6 weeks. Processing time for each subject is expected to be ~1 week. Since the study is incorporated into current standard-of-care clinical workflow (e.g.

imaging prior to surgery and followup imaging at time of return clinical visit), we anticipate high subject retention.

h. Strengths – The strength of the study lies in the robust diffusion sequence obtained by way of the recently released “multiband” diffusion MRI sequence. This allows a substantial improvement in resolution and data quality compared to traditional methods. Additionally, the prospective nature allows us to collect not only optimal therapeutic DBS stimulation parameters, but also those which produce unintended side effects. By capturing this additional data, it will help us to shed light on the cause of these unintended effects and potentially improve the pre-operative functional targeting. Lastly, the significant experience of the investigators in functional neuroimaging and deep brain stimulation is a significant benefit in preparing the study design and interpreting the data.

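### A positive motor-segment slope in IV.f cannot by itself separate a motor-segment effect from a general effect of how much GPi is stimulated, because whole-GPi overlap is never related to outcome

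*Combined protocol and SAP*

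**What the plan says.** Section IV.f labels the GPi by its strongest connection: "Each GPi voxel will then be assigned to the one target with the greatest number of propagated paths". Ten target regions are listed, the last being "8) globus pallidus externus, (9) pedunculopontine nucleus, and (10) subthalamic nucleus". After surgery, "The amount of overlap between the volume of activated tissue (VAT) and each GPi segment will be calculated". The outcome analysis follows: "Linear regression analysis will be performed to determine the degree of improvement in tremor score and degree of overlap between the VAT and each GPi"; the overlaps meant are those with the individual segments. The hypothesis singles out one segment: "We hypothesize greater overlap between the VAT and GPi segment maximally connected to the primary motor cortex will result in a greater improvement".

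The plan does not say whether segments are fitted one at a time or jointly. It states no contrast between segments and brings in no whole-GPi term.

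Aim 3 treats the results as preliminary evidence for replacing atlas-based targeting with functional targeting. Aim 3a assesses VAT overlap on the atlas-based target as well as on the functional target, but does not relate the atlas overlap to improvement. On sample size, IV.c says: "A sample size of ten was chosen based on expected recruitment possibilities and sufficient size to prove feasibility and estimate power size for subsequent studies". It gives no alpha, power or effect size.

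**The concern.** Section II rejects structural targeting in general terms: "Perhaps most concerning regarding all methods of structural localization is the assumption that brain function is predictable by brain structure". The natural rival to the functional hypothesis is therefore structural: benefit depends on how much of the GPi is stimulated, wherever in the GPi that is. Under that rival, motor overlap would still rise with improvement, because motor overlap and whole-GPi overlap move together when a VAT lies partly outside the nucleus or when VATs differ in size.

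If the motor slope is then taken as support for the functional map, the pilot passes on two things to the next study: a case for funding, and an effect estimate for power calculation. Both could reflect the GPi outline alone. IV.i names small size, few poor outcomes and short follow-up as limitations, but not this explanation.

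**Working it through.** **Inputs from the protocol.** One label per GPi voxel, overlap by segment, up to ten segments, and n = 10 (IV.c and IV.f). The sample size has no stated statistical basis, so there is no figure to reproduce.

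**Step 1: the identity.** Let M be motor overlap, G whole-GPi overlap, and Sk overlap with segment k. One label per voxel gives G = S1 + S2 + ..., with M one of the terms.

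**Step 2: the slope under the rival.** Suppose improvement is Y = a + bG + error, with no motor-specific effect. The slope of Y on M is then b × cov(M,G) / var(M), which is positive whenever b and cov(M,G) are. The expected correlation of Y with M is r × corr(M,G), where r = corr(Y,G).

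**Step 3: size under assumed geometry.** None of these inputs is in the documents:
- GPi as an ellipsoid with semi-axes 3 x 7 x 5 mm, one half labelled motor
- VAT as a sphere of radius 2.5-4 mm
- lead scatter SD 1-2 mm per axis, around a point 3 mm inside the motor half (base case) or 1.5 mm inside it
- two-sided alpha 0.05

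In the base case corr(M,G) is 0.85-0.95. At r = 0.7 the expected correlation of Y with M is 0.7 × 0.85 = 0.595 to 0.7 × 0.95 = 0.665. The critical correlation at n = 10 is 0.632. By Fisher's z, power is 45% at a true correlation of 0.6 and 63% at 0.7, so about half of pilots should reach p<0.05. Simulation agrees. Pilots with a positive motor slope at p<0.05, when only G matters:

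| Setting (absolute overlap) | Share of pilots |
|---|---|
| Border 3 mm from target, r = 0.7 | 52-63% |
| Border 1.5 mm, r = 0.5 | 18-20% |
| Border 3 mm, r = 0.3 | about 11% |
| Nominal, one direction | 2.5% |

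Dividing overlap by VAT volume does not remove the effect. The figures are then 50-55% (r = 0.7) and 23-27% (r = 0.5) with the border at 3 mm, and 10-31% with it at 1.5 mm.

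**Step 4: a different model.** Take G from Beta(4,2) and M = G × motor share, with mean share 0.3-0.5, varying between patients. With G explaining 30%, 50% or 70% of outcome variance, the motor slope is significantly positive in 12-32%, 18-55% and 26-78% of pilots. When G has no effect the figure is 2.3-2.8%.

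**Step 5: do the other segment regressions settle it?** With four segments, mean motor share 0.5 and no segment mattering more than another, the motor segment alone was significantly positive in 17%, 25% and 30% of pilots at R² = 0.3, 0.5 and 0.7. A joint fit of ten segments needs 10 + 1 = 11 parameters for ten patients and cannot be estimated.

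**Step 6: candidate remedies.** When the motor segment truly drives benefit (r = 0.7), the planned regression detects it in about 70% of pilots.
- *Motor coefficient adjusted for G:* about 2-3% false positives when only G matters, but only about 10-35% power when the motor segment matters. With one covariate at n = 10, the partial correlation must exceed 0.67 to reach p<0.05.
- *Motor share, M/G, as sole predictor:* significantly positive in only 1-3% of base-case pilots when the motor segment truly matters (11-15% with the border at 1.5 mm). In the base case the share averages 0.89-0.95 and barely varies.
- *Leave-one-out comparison of the M and G models:* picks the right one only about 62-69% of the time in the base case.

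**The case against.** Five points on the other side deserve weight.

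- *There is no test to inflate.* The plan sets no alpha and no success criterion, and IV.i expects that significance may not be reached. This stands. A reader might infer that the pilot will declare false support for functional targeting, but the documents contain no such rule. The link comes from reading the IV.f hypothesis together with Aim 3, and the percentages above describe a conventional test that the plan does not specify.
- *Whole-GPi overlap is available.* This stands: it is the sum of outputs already planned. What is missing is its relation to outcome, not the measurement.
- *A structural comparator exists.* Aim 3a includes the atlas-based target, and Aim 3 is about replacing atlas methods rather than beating the GPi outline. This stands in part. The comparison is of overlap only, and the atlas target is not the whole GPi.
- *The geometry is stylised.* The ellipsoid gives every patient the same GPi and the same motor half, whereas Aim 2 expects variation between patients, which would lower the correlation of M with G. This stands as to size. The Beta model lets the motor share vary and keeps the direction.
- *Malposition may be rare here.* Section II says that 46% of patients "with poor response to DBS therapy have malpositioned DBS leads". A reader might infer that inside/outside variation will dominate this cohort. The figure describes poor responders, and IV.i expects few if any in this study. If nearly all VATs lie inside the GPi, that path is weak, although differing VAT size can still move M and G together.

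**Conclusion.** The gap is real and modest: a cheap improvement to the analysis plan. As written, a positive motor slope does not distinguish a motor-segment effect from a whole-GPi effect, and neither the separate segment fits nor the Aim 3a comparison fills that gap. With a whole-GPi effect only and r of 0.5 to 0.7, a significantly positive motor slope appears in roughly 18-63% of ten-patient pilots under the ellipsoid model with absolute overlap. It is less with a weaker effect, or with overlap as a fraction of VAT volume and the border close to the target. The direction held in every setting with a whole-GPi effect; the size depends on geometry and effect strength that the documents do not give.

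The working does not show that the functional hypothesis is wrong, or that a ten-patient analysis could be made to decide between the two explanations. The adjusted estimate removes the false support but is too imprecise at n = 10 to be more than descriptive.

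**What to change.** In IV.f:

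1. Sum the segment overlaps for each VAT to obtain whole-GPi overlap.
2. Report the slope and fit of improvement on whole-GPi overlap, with confidence intervals, beside those for the motor segment.
3. Report the motor coefficient adjusted for whole-GPi overlap, with its interval, as a descriptive estimate.
4. State that a motor slope alone is not evidence for functional over structural targeting, and that ten patients are unlikely to separate the two.

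Do not make motor share of the in-GPi VAT the main predictor, and do not make a leave-one-out win the criterion for supporting Aim 3. Both perform poorly at this sample size.

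The cost is a few lines of plan text and a small addition to the regression output; no scan, visit or patient is added. The downside is a more cautious Aim 3 conclusion, since the adjusted motor estimate has only about 10-35% power at r = 0.7. For planning the follow-up study, 80% power for the adjusted coefficient would need about 86, 31 or 15 patients at partial correlations of 0.3, 0.5 or 0.7 (Fisher's z, two-sided 0.05, one covariate).

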** All programming settings will be collected throughout the duration of the study, including intra-operative and peri-operative programming/testing
